#### **4.0 SUBJECT SCREENING AND REGISTRATION PROCEDURES**

Patient registration for this trial will be centrally managed by the Oncology Clinical Trials Support Unit (i.e. the Coordinating Center) of The University of Michigan Rogel Cancer Center as described below:

A potential study subject who has been screened for the trial and who has signed the Informed Consent document will be initially documented by the participating site on a Screening and Enrollment Log.

It is the responsibility of the local site investigator to determine patient eligibility prior to submitting patient registration request to the Coordinating Center. After patient eligibility has been determined, a copy of the completed Eligibility Worksheet together with all the pertinent redacted source documents will be submitted by the requesting site to the Coordinating Center, by email to [[contact]](mailto:[contact]).

A Multi-Site Coordinator of the Coordinating Center, who acts as the registrar, will review the submitted documents and process the registration. Sites should inform the Multi-Site Coordinator of a potential registration by 5 p.m. on the day prior to registration. Same day registrations cannot be guaranteed.

The registrar will send an email to the requesting site registrar to confirm patient registration and to provide the study identification number assigned to the patient. In addition, a copy of the

completed Eligibility Worksheet signed and dated by the registrar will be sent back to the requesting site registrar.

Patients found to be ineligible for participation after being consented will be considered screen failures and documented as such in the Screening and Enrollment Log. These patients will not have study identification number assigned to them and will not receive study treatment.

Patients will be enrolled to cohort 1 if they have a leiomyosarcoma or liposarcoma. All other sarcoma histologies will be enrolled to cohort 2. All patients receive the same treatment.

## 5.0 TREATMENT PLAN

### 5.1 Treatment Dosage and Administration

Protocol treatment must start within 14 business days of registration to the study.

Trabectedin 1.1 mg/m^2 will be administered intravenously over a 24-hour continuous infusion once every 21 days. Actual body weight from screening will be used to calculate dose. If weight changes by more than 10% from baseline, recalculate the dose.

Olaparib 150 mg tablets will be taken orally twice daily with a cycle length of 21 days. Olaparib should be taken at the same time every day, 12 hours apart with one glass of water. Olaparib can be taken with or without food. Tablets should be taken whole, not crushed or mixed into food. It is prohibited to consume grapefruit juice while on olaparib therapy. If vomiting occurs shortly after the olaparib tablets are swallowed, the dose should only be replaced if all of the intact tablets can be seen and counted. Should any patient enrolled on the study miss a scheduled dose for whatever reason (e.g., as a result of forgetting to take the tablets or vomiting), the patient will be allowed to take the scheduled dose up to a maximum of 2 hours after that scheduled dose time. If greater than 2 hours after the scheduled dose time, the missed dose is not to be taken and the patient should take their allotted dose at the next scheduled time.

Patients will be requested to maintain a medication diary of each dose of medication. The medication diary should be returned and/or reviewed by clinic staff at each scheduled clinic visit during the course of treatment.

REGIMENT DESCRIPTION					
Agent	Pre-medications; Precautions	Dose	Route	Schedule	Cycle Length
Trabectedin	Pre-medicate with dexamethasone 20 mg IV approximately 30 min prior to trabectedin. Pre-medicate with palonosetron 0.25 mg IV (or similar anti-emetic per institutional guidelines) prior to trabectedin	1.1 mg/m 	IV continuous infusion over 24 hours (+/- 2 hours)	Day 1	3 weeks (21 days)
Olaparib	It is prohibited to consume grapefruit, grapefruit juice and Seville oranges for duration of therapy. No routine prophylactic anti-emetic treatment is	150 mg	PO	BID, continuous	

	required; however, patients should receive appropriate anti-emetics in accordance with local treatment practice guidelines. Alternatively, olaparib tablets can be taken with a light meal/snack (i.e. 2 pieces of toast or biscuits).				
--	--	--	--	--	--

## 5.2 Toxicities and Dosing Delays/Dose Modifications

Any patient who receives treatment on this protocol will be evaluable for toxicity. Each patient will be assessed for the development of toxicity according to the Time and Events Table (Section 6.2). Toxicity will be assessed according to the NCI Common Terminology Criteria for Adverse Events (CTCAE), version 5.0. Dose adjustments should be made according to the system showing the greatest degree of toxicity. Any toxicity observed during the course of the study could be managed by interruption of the dose of study treatment or dose reductions. Repeat dose interruptions are allowed as required, for a maximum of 4 weeks on each occasion. If the interruption is any longer, the study team must be informed. Once dose is reduced, escalation is not permitted

Table 1. Dose Level Reductions of Trabectedin and Olaparib

Dose Levels	Trabectedin	Olaparib
1 (starting)	1.1 mg/m 	150 mg BID
-1	0.94 mg/m 	100 mg BID
-2	0.8 mg/m 	

Criteria for start of new cycle:

- Platelet  $\geq$  100,000/microliter
- Absolute neutrophil count  $\geq$  1000/microliter
- Hemoglobin  $\geq$  9g/dl
- Total bilirubin  $\leq$  1.5 upper limit of normal (ULN)
- Aspartate aminotransferase (AST) and alanine aminotransferase (ALT)  $\leq$  2.5 x ULN
- Alkaline phosphatase (ALP)  $\leq$  2.5 x ULN
- Creatine phosphokinase (CK)  $\leq$  2.5 x ULN
- All non-hematologic toxicities considered related to study treatment must be  $\leq$  grade 2
- Absence of any subjectively intolerable grade 2 adverse event not controlled by supportive therapy

If a patient does not meet criteria to initiate a new cycle of treatment within 28 days of initial medication hold, or requires more than two dose reductions of trabectedin or one dose reduction of olaparib, they should be removed from study treatment.

For hematologic toxicities which meet parameters for dose hold, medication should be held per guidance below. Medication should be resumed at the reduced dose designated below. If AE is recurrent/persistent despite dose reduction as specified below, drug should be discontinued.

Table 2. Criteria for Dose modification of Thrombocytopenia, Neutropenia and Leukopenia

Laboratory Result	Dose Adjustments
Grade 2 Thrombocytopenia	
 
• If does not cause clinically significant symptoms or require a platelet transfusion, continue treatment at current dose and monitor blood counts weekly.
 
• If clinically significant symptoms, hold olaparib. When symptoms resolve and platelets recover to grade 1 (for a maximum of 4 weeks), may resume treatment at any time during the cycle at current dose.
 

Grade 3 Thrombocytopenia	
 
• Interrupt dosing of olaparib for up to 4 weeks and perform at least weekly blood counts.
 
• If platelet count recovers to grade 1 or better within one week and does not cause clinically significant symptoms or require a transfusion, resume olaparib at reduced dose upon recovery or at start of next cycle, and trabectedin at current dose at start of next cycle.
 
• If platelet recovery to CTCAE grade 1 or better occurs within > 1 week-4 weeks, or causes clinically significant symptoms or requires a transfusion, hold olaparib for the remainder of the cycle and reduce olaparib and trabectedin by one dose level at first occurrence at the start of the next cycle. At second recurrence of recovery within >1 week-4 weeks, clinically significant symptoms or transfusion, hold olaparib for the remainder of the cycle and reduce trabectedin by one dose level at the start of the next cycle.
 

Grade 4 Thrombocytopenia	
 
• Interrupt dosing of olaparib for up to 4 weeks and perform at least twice weekly blood counts until platelets improve to grade 3 and then at least weekly.
 
• At first occurrence, if platelet count recovers to grade 1 or better within one week and does not cause clinically significant symptoms or require a transfusion, resume olaparib at reduced dose upon recovery or at start of next cycle. If recovery occurs within >1 week-4 weeks, hold olaparib for the remainder of the cycle. Reduce olaparib and trabectedin by one dose level at the start of next cycle.
 
• At second recurrence of any length, hold olaparib for the remainder of the cycle and reduce trabectedin by one dose level at the start of the next cycle.
 

Grade 4 Neutropenia	
 
• Interrupt dosing of olaparib for up to 4 weeks and perform at least weekly blood counts.
 
• If neutrophil counts increase to <math>\geq 1000/\text{microliter}</math> within one week and is not associated with fever or infection, resume olaparib at reduced dose upon recovery or at next cycle, and trabectedin at current dose level at start of next cycle.
 
• If neutrophil count recovery to CTCAE grade 2 or
 

Laboratory Result	Dose Adjustments
	better occurs within > 1 week-4 weeks, or is associated with fever or infection, hold olaparib for the remainder of cycle and reduce Olaparib and trabectedin by one dose level at first occurrence at the start of the next cycle. At second recurrence of recovery to grade 2 within >1week-4 weeks, or is associated with fever or infection, hold olaparib for the remainder of cycle and reduce trabectedin by one dose level at the start of the next cycle.

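### Section 5.2 gives conflicting instructions for recurrent hematologic toxicity, so the same patient can be removed, have one drug stopped, be reduced or be left unchanged, depending on the reading

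*Combined protocol and SAP*

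**What the plan says.** **General text of section 5.2.** Table 1 lists trabectedin at 1.1, 0.94 and 0.8 mg/m² and olaparib at 150 and 100 mg BID. Below the criteria for starting a cycle, a patient who "requires more than two dose reductions of trabectedin or one dose reduction of olaparib, they should be removed from study treatment". The next paragraph, which concerns hematologic toxicity, says "Medication should be resumed at the reduced dose designated below" and then "If AE is recurrent/persistent despite dose reduction as specified below, drug should be discontinued".

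**Table 2, rapid uncomplicated recovery.** For grade 3 thrombocytopenia: "resume olaparib at reduced dose upon recovery or at start of next cycle, and trabectedin at current dose at start of next cycle". The grade 4 neutropenia row has a parallel branch. Neither branch distinguishes a first from a later occurrence.

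**Table 2, slow or complicated course.** For grade 3 thrombocytopenia: "reduce olaparib and trabectedin by one dose level at first occurrence at the start of the next cycle". For grade 4 neutropenia: "hold olaparib for the remainder of cycle and reduce Olaparib and trabectedin by one dose level at first occurrence". On recurrence, only trabectedin is reduced. The grade 4 thrombocytopenia row reads "At second recurrence of any length, hold olaparib for the remainder of the cycle and reduce trabectedin by one dose level", and the grade 3 row begins "At second recurrence of recovery within >1 week-4 weeks, clinically significant symptoms or transfusion, hold olaparib for the remainder of the cycle" before lowering trabectedin. Recurrent complicated grade 4 neutropenia is handled in the same way.

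**Other places.** Table 3 lowers olaparib to 100 mg BID after hemoglobin below 8 g/dl. Table 5 lowers both drugs at a first uncontrolled grade 3 or 4 non-hematologic event. The hematologic management paragraph of section 5.2 and the end of section 5.3 both say that study treatment is to be stopped if febrile neutropenia develops.

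**The concern.** The general text and the tables answer the same event differently, and nothing says which prevails. The toxicities involved are foreseeable: section 1.3 reports thrombocytopenia and prolonged neutropenia as the dose-limiting toxicities of this combination in the phase 1b study.

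Two centers take part. Each could follow the text faithfully and act differently on the same patient. That bears first on patient safety. It also affects exposure to the combination, the discontinuation rate and the safety and tolerability objective (2.2.3), because those results would partly reflect how each site read section 5.2. It may bear on response as well, in cohorts of at most 26 and 27 patients where success turns on 5 and 4 responders (section 11.2).

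**Working it through.** No sample-size arithmetic applies. The check counts dose levels and then traces patients through the text.

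**1. Permitted reductions against Table 1.** Trabectedin: 3 levels − 1 = 2 reductions. Olaparib: 2 levels − 1 = 1 reduction. This matches the removal rule if it is read as more than two for trabectedin and more than one for olaparib. The sentence can also be parsed as removal at the first olaparib reduction, but then the 100 mg BID level and every row that resumes reduced olaparib would be pointless.

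**2. Recurrence in a patient already at olaparib 100 mg BID.** The milder recurrence is rapid and uncomplicated (grade 3 thrombocytopenia or grade 4 neutropenia). The worse recurrence is a complicated event or grade 4 thrombocytopenia. Two phrases are open:

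- Resuming olaparib at a reduced dose means either a further step down or staying at 100 mg BID.
- The discontinuation sentence governs always, or only where Table 2 gives no recurrence instruction, or only once every level has been used.

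For this trace, discontinuation is taken to end study treatment, although the sentence names no drug.

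| Reduced dose means | Discontinuation applies | Milder recurrence | Worse recurrence | Result |
|---|---|---|---|---|
| further step | always | stop | stop | contradicts Table 2 |
| further step | where table silent | stop | continue | inversion |
| further step | after all levels | stop | continue | inversion |
| 100 mg BID | always | stop | stop | contradicts Table 2 |
| 100 mg BID | where table silent | stop | continue | inversion |
| 100 mg BID | after all levels | continue | continue | no conflict |

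That is 2 direct contradictions, 3 inversions and 1 combination without conflict.

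**3. First event of a second toxicity.** Olaparib is at 100 mg BID after anemia (Table 3). A first complicated grade 3 thrombocytopenia then orders both drugs down one level.

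- Taken literally, olaparib reductions required = 1 + 1 = 2, which exceeds 1, so the patient is removed. Trabectedin has not yet been reduced.
- If the olaparib part lapses at its lowest level, or if occurrences are counted per drug across toxicities, only trabectedin is reduced and treatment continues.
- For comparison, a patient whose complicated thrombocytopenia recurs needs 1 olaparib reduction and 1 + 1 = 2 trabectedin reductions. Both are within the limits, so the patient continues.

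The first-occurrence row of Table 5 raises the same question.

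**4. Counting words.** Table 2 passes from a first occurrence to a second recurrence. If that means the third event, the second event has no instruction in those rows.

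**5. Febrile neutropenia.** Table 2 lets a patient with febrile grade 4 neutropenia go on at reduced levels. The stopping sentences in sections 5.2 and 5.3 do not say whether the stop is temporary or permanent.

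**The case against.** Much of section 5.2 is coherent. The removal limits match Table 1 on their natural reading, and the recurrence rows lower only trabectedin, which respects the single olaparib step. Table 2 uses different phrases for resuming at a reduced dose and for going down one level, so the first may simply mean 100 mg BID. The discontinuation sentence may apply only after the table's reductions are used up. Stopping for febrile neutropenia may mean a pause, since section 5.2 goes on to mention G-CSF in later cycles. All of this stands. It shows that one conflict-free reading of the recurrence rules exists, but the protocol does not tell sites to adopt it.

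Four stronger conclusions might be inferred, and the documents do not support them:

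- **The plan always treats a milder recurrence more drastically.** This happens only on some readings, as the table above shows.
- **Removal at a first event of a second toxicity is a contradiction.** Taken literally, the two rules combine into one action. Objecting that trabectedin levels remain unused is a clinical preference. The gap is that the row does not say what its olaparib part means at the lowest level.
- **Power falls by a calculable amount.** The documents give neither the frequency of second events nor the loss of response after removal, and they do not say whether the 25% and 20% targets already allow for toxicity removals. Any power figure would rest on invented inputs.
- **Removal before the first restaging forfeits most of the chance of a response.** Section 6.2 asks for an end-of-treatment scan if progression has not been shown radiographically, and section 7.1.1 counts a patient with one cycle and a re-evaluation as evaluable.

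**Conclusion.** The concern holds as a conflict in the current wording. The firmest part is the general sentence that discontinues an unnamed drug on recurrence, set against the Table 2 rows that continue treatment for such a recurrence. Next are the rows that call for reduced olaparib when no lower level exists, and the febrile neutropenia sentences set against the febrile branch of Table 2.

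The size can be stated only as a count of readings: five of the six combinations leave a contradiction or an inversion. That count is not a probability, and it rests on the two sets of readings listed and on treating discontinuation as the end of study treatment. How many patients would be affected, and the effect on response or power, cannot be derived from the documents. The point should be settled because it concerns the regimen's known dose-limiting toxicities and consistent treatment across the two centers.

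**What to change.** Reconcile the general text of section 5.2 with Tables 1, 2, 3 and 5 and with the febrile neutropenia sentences in sections 5.2 and 5.3, so that one action follows from each state. The amendment should state:

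- whether the olaparib limit means removal at the first or at a second required reduction;
- whether occurrences are counted per toxicity or per drug, and which event a second recurrence is;
- which drug the discontinuation sentence means, and when it applies relative to Table 2;
- what the olaparib part of each row means once olaparib is at its only lower level, including the rapid-recovery branches that have no occurrence limit;
- whether stopping for febrile neutropenia is temporary or permanent, and how it relates to Table 2.

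The choice of clinical rule is the sponsor's. The cost is one protocol amendment to wording, with no added visits, tests or patients.

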#### **Management of hematologic toxicities while on study treatment**

Adverse event of neutropenia and leukopenia should be managed as deemed appropriate by the investigator with close follow up and potential interruption of study drug if CTC grade 3 or worse neutropenia occurs as above. Primary prophylaxis with Granulocyte colony-stimulating factor (G-CSF) is not recommended for first cycle, however, if a patient develops febrile neutropenia, study treatment should be stopped and appropriate management including G-CSF should be given according to local hospital guidelines if felt to be clinically appropriate and in subsequent cycles.

Platelet transfusions, if indicated, should be done according to local hospital guidelines. Appropriate supportive treatment and causality investigation should be performed as indicated clinically.

#### **Management of anemia**

Table 3. Management of anemia

Hemoglobin	Action to be taken
Hb < 10 but $\geq$ 8 g/dl (CTCAE Grade 2)	
First occurrence:
 
Give appropriate supportive treatment and investigate causality. Investigator judgement to continue study treatment with supportive treatment (e.g. transfusion) or interrupt olaparib for a maximum of 4 weeks. Study treatment can be restarted if Hb has recovered to <math>\geq</math> 9g/dl.

	
Subsequent occurrences:
 
If Hb < 10 but <math>\geq</math> 9 g/dl investigator judgement to continue olaparib with supportive treatment (e.g. transfusion) or dose interrupt (for max of 4 weeks) and upon recovery dose reduction of olaparib may be considered (to 100 mg twice daily).
 
If Hb < 9 but <math>\geq</math> 8 g/dl, interrupt olaparib (for max of 4 weeks) until Hb <math>\geq</math> 9 g/dl and upon recovery dose reduction of olaparib may be considered (to 100 mg twice daily).

Hb < 8 g/dl (CTCAE Grade 3)	
Give appropriate supportive treatment (e.g. transfusion) and investigate causality.
 
Interrupt olaparib for a maximum of 4 weeks until improved to Hb <math>\geq</math> 9 g/dl.
 
Upon recovery dose reduce olaparib to 100 mg twice daily.

#### **Management of prolonged hematological toxicities while on study treatment**

If a patient develops prolonged hematological toxicity such as:

- $\geq$ 2-week interruption/delay in study treatment due to CTC grade 3 or worse anemia and/or development of blood transfusion dependence
- $\geq$ 2-week interruption/delay in study treatment due to CTC grade 3 or worse neutropenia (ANC <  $1 \times 10^9/L$ )

- $\geq 2$ -week interruption/delay in study treatment due to CTC grade 3 or worse thrombocytopenia and/or development of platelet transfusion dependence (Platelets  $< 50 \times 10^9/L$ )

Check weekly differential blood counts including reticulocytes and peripheral blood smear. If blood parameter abnormalities remain clinically abnormal after 4 weeks of dose interruption, the patient should be referred to a hematologist for further investigations. Bone marrow analysis and/or blood cytogenetic analysis should be considered at this stage according to standard hematological practice. Study treatment should be discontinued if blood counts do not recover to CTC grade 1 or better within 4 weeks of dose interruption.

Development of a confirmed myelodysplastic syndrome or other clonal blood disorder should be reported as an SAE and full reports must be provided by the investigator to AstraZeneca Patient Safety. Study treatment should be discontinued if patient's diagnosis of MDS and/or AML is confirmed.

Common treatable causes of anemia (e.g., iron, vitamin B12 or folate deficiencies and hypothyroidism) should be investigated and appropriately managed. In some cases, management of anemia may require blood transfusions. For cases where patients develop prolonged hematological toxicity ( $\geq 2$ -week interruption/delay in study treatment due to CTC grade 3 or worse anemia and/or development of blood transfusion dependence, refer to guidance earlier in this section for the management of this.

Table 4. Criteria for Dose Modification of Non-Hematologic Laboratory Adverse Events

Laboratory Result	Dose Adjustments
Total bilirubin $> 1.5 \times$ ULN*	
 
• Hold trabectedin and olaparib
 
• Monitor weekly total bilirubin until recovery to <math>\leq 1.5 \times</math> ULN, and then resume olaparib at current dose upon recovery.
 
• If peak bilirubin <math>\leq 3 \times</math> ULN, reduce trabectedin by one dose level at start of next cycle.
 
• At second recurrence, reduce trabectedin by next dose level
 
• If third recurrence or peak bilirubin <math>> 3 \times</math> ULN, permanently discontinue study treatment
 

AST or ALT* $> 2.5 \times$ ULN	
 
• Hold trabectedin and olaparib
 
• Monitor weekly LFTs until recovery <math>\leq 2.5 \times</math> ULN and then resume olaparib at current dose upon recovery.
 
• If peak value <math>> 2.5 \times</math> ULN and <math>\leq 5 \times</math> ULN, resume trabectedin at same dose at start of next cycle.
 
• If peak value <math>> 5 \times</math> ULN, reduce trabectedin by one dose level
 
• At second recurrence of peak value <math>> 5 \times</math> ULN, reduce trabectedin by one dose level.
 

ALP $> 2.5 \times$ ULN	
 
• Hold trabectedin
 
• Monitor weekly ALP until recovery to <math>\leq 2.5 \times</math> ULN
 
• Reduce trabectedin by one dose level
 
• At second occurrence, reduce trabectedin by one dose level
 

CK $> 2.5 \times$ ULN	
 
• Hold trabectedin
 
• Monitor weekly CK until recovery
 
• If peak value <math>> 2.5 \times</math> ULN-<math>5 \times</math> ULN, resume trabectedin at same dose.
 
• If peak value <math>> 5 \times</math> ULN, reduce trabectedin by one dose level
 
• At second occurrence of peak value <math>> 5 \times</math> ULN, reduce trabectedin by one dose level
 

\*In case a patient shows an AST or ALT  $\geq 3 \times \text{ULN}$  together with total bilirubin  $\geq 2 \times \text{ULN}$  please refer to Appendix A 'Actions required in cases of increases in liver biochemistry and evaluation of Hy's Law', for further instructions.

Table 5. Criteria for Dose modification of Non-Hematologic Adverse events

Adverse Event	Dose Adjustment
Grade 2 toxicity that is subjectively intolerable and not controlled by optimal supportive medication	
 
Interrupt dosing for up to 4 weeks. May resume olaparib at current dose or reduced dose when toxicity improves to tolerable or grade 1 at first recurrence.
 
Upon resumption of study treatment, can continue trabectedin at current dose or reduce by one dose level at first occurrence at the start of the next cycle. At second recurrence, reduce trabectedin by one dose level at the start of the next cycle
 
Patient to be withdrawn from study if unable to resume within 4 weeks
 

Grade 3 or 4 toxicity not controlled by optimal supportive medication	
 
Interrupt dosing for up to 4 weeks. Do not resume olaparib until start of next cycle.
 
Upon resumption of treatment, reduce trabectedin and olaparib by one dose level at first occurrence. At second recurrence, reduce trabectedin by one dose level
 
Patient to be withdrawn from study if unable to resume within 4 weeks
 

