### 3.1 Inclusion Criteria

- 3.1.1 Advanced unresectable or metastatic sarcoma
  - Cohort 1: LMS/LPS
  - Cohort 2: Other histologies (excluding Gastrointestinal Stromal Tumors)
- 3.1.2 Must have received at least 1 prior standard systemic therapy regimen. For cohort 1 patients, this must have included a prior anthracycline.
- 3.1.3 Measurable disease by RECIST 1.1 criteria
- 3.1.4 Age  $\geq$  16 years
- 3.1.5 ECOG  $\leq$  1
- 3.1.6 Adequate hematologic, renal and hepatic function within 14 days prior to administration of study treatment as defined below:

Hemoglobin	$\geq 10$ g/dL with no blood transfusion within 28 days
Absolute neutrophil count	$\geq 1.5 \times 10^9$ /L
Platelets	$\geq 100 \times 10^9$ /L

Total Bilirubin	$\leq 1.5 \times$ institutional upper limit of normal (ULN).  NOTE: patients with elevated bilirubin secondary to Gilbert's disease are eligible to participate ( $<2.0 \times$ ULN should be used)
Aspartate aminotransferase (AST) & alanine aminotransferase (ALT)	$\leq 2.5 \times$ institutional ULN unless liver metastases are present in which case AST and ALT must be $\leq 5 \times$ ULN
Serum creatinine	Estimated or calculated creatinine clearance (Cockcroft-Gault formula) $\geq 51$ mL/min using the Cockcroft-Gault equation or based on a 24-hour urine test:  Estimated creatinine clearance = $(140 - \text{age} [\text{years}]) \times \text{weight} (\text{kg}) \times F^a$ serum creatinine (mg/dL) $\times 72$ a where F=0.85 for females and F=1 for males.

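### At week 4 of a hold for severe anemia or grade 4 neutropenia, Section 5.2 both stops and continues the same patient; separately, its new-cycle liver limits block patients whom 3.1.6 admits

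*Combined protocol and SAP*

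**What the plan says.** **Blood counts.** In Section 5.2, the subsection on prolonged hematological toxicities covers interruptions of at least two weeks for grade 3 or worse anemia, neutropenia or thrombocytopenia. It ends: "Study treatment should be discontinued if blood counts do not recover to CTC grade 1 or better within 4 weeks of dose interruption". For anemia it adds "refer to guidance earlier in this section for the management of this".

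Two tables in the same section also run to 4 weeks:

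- Table 3, hemoglobin below 8 g/dL: interrupt olaparib for at most 4 weeks until hemoglobin is at least 9 g/dL, then "Upon recovery dose reduce olaparib to 100 mg twice daily". The same table labels 8 to below 10 g/dL as grade 2.
- Table 2, grade 4 neutropenia: if recovery to grade 2 or better takes more than one week and up to 4 weeks, hold olaparib for the rest of the cycle and "reduce Olaparib and trabectedin by one dose level at first occurrence at the start of the next cycle".

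**Liver.** Item 3.1.6 limits AST/ALT to 2.5×ULN "unless liver metastases are present in which case AST and ALT must be" at most 5×ULN. It limits bilirubin to 1.5×ULN, or below 2.0×ULN with Gilbert's disease. The criteria for starting a new cycle in 5.2 require AST/ALT at most 2.5×ULN and bilirubin at most 1.5×ULN, with no exception for either group. The removal rule begins "If a patient does not meet criteria to initiate a new cycle of treatment within 28 days of initial medication hold" and says that such a patient should come off study treatment.

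**The concern.** The first problem is two opposite instructions for one patient. In a two-center trial, one site can follow Table 2 or 3 and continue at a reduced dose, while the other follows the prolonged-toxicity subsection and stops both drugs. Neither would be deviating from the text it read.

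The second is an entry criterion that the dosing rules cannot honor. The protocol deliberately admits two groups with raised baseline liver values, then prevents them from starting cycle 2 on those same values. They lose treatment without any toxicity. Under 7.1.1 such a patient can still count as evaluable for response after one cycle and a repeat scan.

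**Working it through.** The plan prints no figure to reproduce here. The check sets its thresholds side by side.

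**1. Patient still off drug at 4 weeks, first occurrence**

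| State at 4 weeks | Prolonged-toxicity rule | Table 2 or 3 | Clash |
|---|---|---|---|
| Hb ≥10 after Hb <8 g/dL | may continue | restart olaparib 100 mg BID | no |
| Hb 9.0 to <10 after Hb <8 (grade 2) | stop study treatment | restart olaparib 100 mg BID | **yes** |
| Hb 8 to <9 (grade 2) | stop | restart level not reached within the 4 weeks allowed | no |
| Neutrophils grade 2 after grade 4 | stop | both drugs down one level | **yes** |
| Neutrophils grade 2 after grade 3 | stop | no row in Table 2 | no |
| Platelets grade 2 after grade 3 or 4 | stop | grade 1 required | no |

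Platelets show the two parts agreeing. Table 2 opens its recovery condition with "If platelet count recovers to grade 1 or better within one week" and keeps grade 1 for slower recovery, as the prolonged-toxicity rule does. Only anemia and grade 4 neutropenia are out of line.

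What turns on the choice of rule, using the dose levels in Table 1:

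- Olaparib: (150 − 100)/150 = 33.3% reduction, or stop.
- Trabectedin after grade 4 neutropenia: (1.1 − 0.94)/1.1 = 14.5% reduction, or stop.
- Trabectedin after anemia: no reduction in Table 3, or stop.

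**2. Liver values unchanged from baseline**

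| Test | Entry limit (3.1.6) | New-cycle limit (5.2) | Admitted but blocked |
|---|---|---|---|
| AST/ALT, liver metastases | ≤5×ULN | ≤2.5×ULN | >2.5 to 5×ULN |
| Bilirubin, Gilbert's disease | <2.0×ULN | ≤1.5×ULN | >1.5 to <2.0×ULN |
| ALP | none | ≤2.5×ULN | >2.5×ULN |

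Timing with 21-day cycles:

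- Cycle 2 day 1 = 1 + 21 = day 22. The patient fails here at the latest.
- Removal at about 22 + 28 = day 50.
- Trabectedin doses received: at most 1. The 18-month maximum would allow about 18 × 30.44/21 = 26.1 cycles.

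The plan does not say whether the new-cycle criteria apply to cycle 1. If they do, the patient receives no dose.

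**3. Is there an exception elsewhere?** Appendix A makes allowance for patients who were abnormal before treatment, but only for Hy's Law follow-up. It refers liver management back to Section 5.2, so it gives no dosing exception. Sections 8.1 and 8.2.1 treat an unchanged baseline abnormality as pre-existing. That bears on whether Table 4, which is headed as adverse events, applies to such a patient. It does not relax the new-cycle limits.

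**The case against.** **The prolonged-toxicity rule is the specific one and overrides the tables.** This is a reasonable reading, but the text does not establish it. The Table 2 and 3 rows run to 4 weeks themselves, so they also address long holds. The cross-reference "refer to guidance earlier in this section for the management of this" could mean the subsection's own opening or Table 3. The instruction to adjust for the system with the greatest toxicity chooses between organ systems, not between two rules for one count.

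**The clash is narrow.** This stands. A patient who reaches hemoglobin 9 g/dL sooner restarts under Table 3 and may never face the week-4 test. Later events fall under a separate sentence: "If AE is recurrent/persistent despite dose reduction as specified below, drug should be discontinued".

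**Stricter limits for retreatment than for entry may be deliberate.** Sections 1.2 and 1.3 list raised ALT or liver enzymes among the adverse events of trabectedin and of the combination. If so, admitting these patients makes little sense, and the entry limit is the one to change. Section 5.2 also says that patients failing for 28 days should be removed, and asks that the study team be told of interruptions longer than 4 weeks. Loss of treatment is therefore the default, not an absolute mandate.

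A reader might infer more than the documents support:

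- *That the new-cycle criteria (Hb ≥9 g/dL, ANC ≥1000/microliter) also contradict the stop rule, so grade 3 neutropenia is affected.* They are necessary conditions for starting a cycle. Meeting them does not cancel a stop rule.
- *That the MDS/AML safeguards are undermined.* Hematology referral and stopping for confirmed MDS/AML are separate sentences, which neither table contradicts. Section 9.2 puts incidence below 1.5% on olaparib monotherapy. Only the grade 1 sentence is in tension.
- *That Table 4 forces dose cuts for stable baseline liver values.* Whether Table 4 reaches those values at all is arguable.

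**Conclusion.** Both points hold in limited form. The first is a stop/continue contradiction with no stated precedence. It is confined to first occurrences still off drug near week 4, with hemoglobin 9.0 to below 10 g/dL after a value below 8, or grade 2 neutrophils after grade 4. Platelets, grade 3 neutropenia, recurrences and earlier restarts are outside it. The second is a mismatch between entry and new-cycle limits. It leaves patients with stable values in the two liver bands at most one trabectedin dose, and ALP has a new-cycle limit but no entry limit.

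The first conclusion relies on Table 3's own grade labels. The second assumes that liver values stay at baseline and that the new-cycle criteria apply from cycle 2. The documents give no rate for any of these situations, so a reader should not infer an effect on the response rate, error rates or power. Severity is minor to moderate. The case for acting is that the text is wrong as written and inexpensive to correct.

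**What to change.** **Blood counts.** Add one sentence to the hemoglobin below 8 g/dL row of Table 3 and to the grade 4 neutropenia row of Table 2: before 4 weeks this table governs; if the patient is still off drug at 4 weeks, the grade 1 rule under prolonged hematological toxicities governs. Replace the vague cross-reference in that subsection with the name of the part meant. If the sponsor intends hemoglobin of at least 9 g/dL and grade 2 neutrophils to suffice, change the prolonged-toxicity sentence instead. Precedence should not be extended to every hold of two weeks or more, because that would keep off drug patients whom Table 3 now restarts in week 2 or 3.

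**Liver.** Choose one of two alignments:

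- Add to the new-cycle criteria and Table 4 an exception only for patients whose baseline already exceeded the standard limit. It should require no clinically relevant rise from baseline, with a stated tolerance for laboratory variation. Cap it at 5×ULN for AST/ALT with liver metastases and below 2.0×ULN for bilirubin with Gilbert's disease. That bilirubin cap stays under the Potential Hy's Law threshold, so Appendix A need not change.
- If dosing at those values is judged unsafe, lower the 3.1.6 limits to the new-cycle limits.

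In either case, align ALP between entry and retreatment.

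**Cost.** A short wording amendment, with no added visits, tests or patients. Under the precedence sentence a few patients stop at week 4; under the lower entry limits a few become ineligible.
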